8.9 Safety

Frequency tables will be used to present the safety outcomes including incidences of TEAEs, SAEs (including deaths), TEAEs leading to death, treatment-emergent AESIs, liver-related TEAEs, TEAEs leading to premature treatment discontinuation, TEAEs leading to premature study withdrawal, TEAEs by relationship and TEAEs by severity.

Change from baseline and incidence of pre-defined treatment-emergent newly occurring abnormalities in vital signs, clinical laboratory test results and ECG results will be summarised. Graphical presentations will also be used to help describe vital signs, selected laboratory test values and ECG parameters.

Other safety outcomes include physical examination [REDACTED]

Safety data collected for the main study phase up to Day 84/Day 90 and the subsequent 4-week FU visit will be included in the data analyses and presented in the CSR. Safety data collected during ET and ET FU will not be included in the data analyses or in the CSR, and will be presented in the report addendum.

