8.9.3 Clinical Laboratory Evaluations

All central laboratory test results will be summarised using descriptive statistics at each visit for observed data and change from baseline.

Based on the laboratory reference range, laboratory test results will be categorised as:

- Low
- Normal
- High

Change from baseline to each post-baseline visit, main study phase EOT and EOS in aforementioned reference range laboratory category will be presented as shift tables. Abnormal laboratory values, categorised per reference range as high or low will be flagged in by-patient data listings.

In addition, pre-defined treatment-emergent abnormalities (newly occurring), as defined by CTCAE criteria, will be presented in tables where the incidence rate will be based on the total number of patients 'at risk':

For example:

- If a CTCAE criterion involves a change from baseline, evaluable patients would have both a pre-dose and at least 1 post-dose value recorded
- If a CTCAE criterion does not consider changes from baseline, to be evaluable the patient need only have 1 post-dose value recorded.

In the event that a laboratory value does not comply with the CTCAE criterion, the laboratory value will be categorised as normal.

In the event of a retest of the same sample due to, for example, a laboratory error (same visit number assigned), the last available assessment will be used for by-visit summaries, including identification of pre-defined treatment-emergent abnormalities (newly occurring), regardless of whether the laboratory assessment for that particular nominal visit is available or not.

The handling of laboratory values below limit of quantification (LOQ) will be described in the detailed SAP for each laboratory test separately.

It should be noted that for glucose, only non-fasting values will be included in any summary presentations although all results will be listed in by-patient listings.

As per the FDA Liver Safety Guidance, the following treatment-emergent incidence tables will be presented, including time-to-event analyses, and by-patient data listings:

- $3 \times$ -, $5 \times$ -, $10 \times$ -, and $20 \times$ ULN elevations of AST, ALT, and either ALT or AST.
- Any elevations of total bilirubin, elevated total bilirubin $> 2 \times$ ULN.
- Any elevations of alkaline phosphatase (ALP) $> 1.5 \times$ ULN.

- Elevation of AST or ALT $> 3 \times$ ULN accompanied by elevated total bilirubin ($> 1.5 \times$ ULN, $> 2 \times$ ULN).

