Blood bilirubin increased	Total bilirubin (μmol/L)	>ULN - 1.5 x ULN if baseline was normal; > 1.0 - 1.5 x baseline if baseline was abnormal	>1.5 - 3.0 x ULN if baseline was normal; >1.5 - 3.0 x baseline if baseline was abnormal	>3.0 - 10.0 x ULN if baseline was normal; >3.0 - 10.0 x baseline if baseline was abnormal	>10.0 x ULN if baseline was normal; >10.0 x baseline if baseline was abnormal	-
CPK increased	Creatine phosphokinase	>ULN - 2.5 x ULN	>2.5 x ULN - 5 x ULN	>5 x ULN - 10 x ULN	>10 x ULN	-
Creatinine increased	Creatinine	>ULN - 1.5 x ULN	>1.5 - 3.0 x baseline; >1.5 - 3.0 x ULN	>3.0 x baseline; >3.0 - 6.0 x ULN	>6.0 x ULN	-
Gamma glutamyl transferase (GGT) increased	GGT (U/L)	>ULN - 2.5 x ULN if baseline was normal; 2.0 - 2.5 x baseline if baseline was abnormal	>2.5 - 5.0 x ULN if baseline was normal; >2.5 - 5.0 x baseline if baseline was abnormal	>5.0 - 20.0 x ULN if baseline was normal; >5.0 - 20.0 x baseline if baseline was abnormal	>20.0 x ULN if baseline was normal; >20.0 x baseline if baseline was abnormal	-
Hypoalbuminemia	Albumin (g/L)	<LLN - 3 g/dL; <LLN - 30 g/L	<3 - 2 g/dL; <30 - 20 g/L	<2 g/dL; <20 g/L	Life-threatening consequences; urgent intervention indicated	Death

Document: \\weedc-vnasc01\BIOSdata\F2G\F901318\

Author:

Version Number:

3.0

Version Date:

06Apr2023

Template No.: CS_TP_BS016 Revision 6

Reference: CS_WI_BS005

Effective Date: 02Dec2019

F2G Ltd.
PROTOCOL F901318/0032

CTCAE Term	Laboratory Test	Grade 1	Grade 2	Grade 3	Grade 4	Grade 5
Activated partial thromboplastin time prolonged	Prothrombin time and activated Partial Thromboplastin Time	>ULN - 1.5 x ULN	>1.5 - 2.5 x ULN	>2.5 x ULN; bleeding	-	-
Hepatic failure		-	-	Asterixis; mild encephalopathy; drug-induced liver injury (DILI); limiting self care ADL	Life-threatening consequences; moderate to severe encephalopathy; coma	Death
INR increased	Prothrombin time and activated Partial Thromboplastin Time	>1.2 - 1.5; >1 - 1.5 x baseline if on anticoagulation; monitoring only indicated	>1.5 - 2.5; >1.5 - 2.5 x baseline if on anticoagulation; dose adjustment indicated	>2.5; >2.5 x baseline if on anticoagulation; bleeding	-	-

Predefined treatment-emergent abnormalities, as defined by CTCAE criteria, will be presented in tables where the incidence rate will be based on the total number of patients ‘at risk’, for example:

- If a CTCAE criterion involves a change from baseline, evaluable patients would have both a pre-dose and at least one post-dose value recorded.

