- If a CTCAE criterion does not consider change from baseline, to be evaluable the patient need only have one post-dose value recorded.

Document: \\weedc-vnasc01\BIOSdata\F2G\F901318\ [Redacted]
 Author: [Redacted] Version Number: 3.0
 Version Date: 06Apr2023
 Template No.: CS_TP_BS016 Revision 6 Reference: CS_WI_BS005
 Effective Date: 02Dec2019

[Redacted]

F2G Ltd.
PROTOCOL F901318/0032

In the event that a laboratory value does not comply with the CTCAE criterion, the laboratory value will be categorised as normal.

18.2.4. [Redacted]

[Redacted]

[Redacted]

[Redacted]

[Redacted]

[Redacted]

[Redacted]

[Redacted]

[Redacted]

Document: \\eedc-vnasc01\BIOSdata\F2G\F901318 [Redacted]

Author: [Redacted] Version Number: 3.0

Version Date: 06Apr2023

Template No.: CS_TP_BS016 Revision 6

Reference: CS_WI_BS005

Effective Date: 02Dec2019

[Redacted]

[REDACTED]

F2G Ltd.
PROTOCOL F901318/0032

[REDACTED]

[REDACTED]

[REDACTED]

[REDACTED]

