18.3.2. ECG CATEGORIES

Markedly abnormal quantitative ECG measurements will be identified in accordance with the following predefined criteria:

[figure not shown]
- Absolute values for QTcF will be classified as:
 - > 450 msec
 - > 480 msec
 - > 500 msec
- Change from Baseline for QTcF will be classified as:
 - > 30 msec increase from Baseline
 - > 60 msec increase from Baseline

Predefined treatment-emergent categories will be presented in tables where the incidence rate will be based on the total number of patients ‘at risk’, for example:

- If a criterion involves a change from baseline, evaluable patients would have both a pre-dose and at least one post-dose value recorded.

Document:	\\weedc-vnasc01\BIOSdata\F2G\F901318\		
Author:		Version Number:	3.0
		Version Date:	06Apr2023
Template No.:	CS_TP_BS016 Revision 6	Reference:	CS_WI_BS005
Effective Date:	02Dec2019		

F2G Ltd.
PROTOCOL F901318/0032

- If a criterion does not consider change from baseline, to be evaluable the patient need only have one post-dose value recorded.
- Central overreads of ECG data began part way through the study. Summaries of QTcF, incidence of prolongation and spaghetti plot for absolute QTcF over time will be provided for ECG prospective central and retrospective central assessments.

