18.4.2. VITAL SIGNS MARKEDLY ABNORMAL CRITERIA

Predefined treatment-emergent abnormalities will be presented in tables where the incidence rate will be based on the total number of patients ‘at risk’, for example:

- If a criterion involves a change from baseline, evaluable patients would have both a pre-dose and at least one post-dose value recorded.
- If a criterion does not consider change from baseline, to be evaluable the patient need only have one post-dose value recorded.

Markedly abnormal quantitative Vital Signs measurements will be identified in accordance with the following predefined markedly abnormal criteria:

Variable (Unit)	Low	High
Systolic Blood Pressure (mmHg)	NA	Hypertension-SBP>=140
Diastolic Blood Pressure (mmHg)	NA	DBP>=80
Pulse rate (BPM)	Sinus bradycardia: <60	Sinus tachycardia: >100 Supraventricular tachycardia: >100 Ventricular tachycardia: >100
Body temperature (°C)	Hypothermia<=35(grade 2)	Fever >=38 (grade 1)
Weight (kg)	Weight Loss- percentage change from baseline ≤ - 5.0 %	Weight Gain- percentage change from baseline ≥ 5.0 %

Document: \\weedc-vnasc01\BIOSdata\F2G\F901318\ [Redacted]
 Author: [Redacted] Version Number: 3.0
 Version Date: 06Apr2023
 Template No.: CS_TP_BS016 Revision 6 Reference: CS_WI_BS005
 Effective Date: 02Dec2019

NA-Not Available.

In the event that a vital sign value does not comply with the criterion for classification as Low or High, the value will be categorised as normal.

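### For absolute safety thresholds, the treatment-emergent tables keep patients already abnormal at baseline in the at-risk denominator, and the SAP states no newly-occurring condition for the numerator

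*SAP*

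**What the plan says.** The protocol (8.9 Safety) plans that the "incidence of pre-defined treatment-emergent newly occurring abnormalities in vital signs, clinical laboratory test results and ECG results will be summarised". Section 8.9.3 repeats the condition for laboratory tests, "pre-defined treatment-emergent abnormalities (newly occurring), as defined by CTCAE criteria", and 8.9.4.1 repeats it for vital signs. Protocol 8.9.4.2 (ECG) does not repeat it, so for QT the condition rests on the general sentence in 8.9. Protocol 8.9.3 also defines treatment-emergent as having started or worsened on or after the first dose.

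The same protocol section sets the denominator: "If a CTCAE criterion does not consider changes from baseline, to be evaluable the patient need only have 1 post-dose value recorded". Protocol 8.9.4.1 and 8.9.4.2 refer back to it for vital signs and ECG.

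The SAP keeps the label but not the condition. SAP 18.2.3 says: "Predefined treatment-emergent abnormalities, as defined by CTCAE criteria, will be presented in tables". Its evaluability rule is "If a CTCAE criterion does not consider change from baseline, to be evaluable the patient need only have one post-dose value recorded". SAP 18.3.2 has "If a criterion does not consider change from baseline, to be evaluable the patient need only have one post-dose value recorded", applied to QTcF above 450, 480 and 500 msec, and 18.4.2 repeats that rule for vital signs. The words newly occurring do not appear in the readable SAP text. No rule there says when a measured value counts as started or worsened, and the readable part of SAP 3.3 lists no change on this point.

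SAP 18.4.2 also lists the high pulse criterion as "Sinus tachycardia: >100 Supraventricular tachycardia: >100 Ventricular tachycardia: >100". It gives no low limit for systolic or diastolic pressure, and any value that is neither low nor high is classed as normal.

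**The concern.** A patient who is already past a threshold before the first dose cannot newly cross it. Keeping such patients in the denominator is wrong for a new-onset rate, and without a stated numerator rule two programmers could produce different tables from the same data. The rule does not even require a baseline value, so for some evaluable patients new onset could not be judged at all.

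Such patients are to be expected. Neutropenia is a host factor in protocol Appendix 2, and neutropenia at screening is a subgroup in SAP 7.4, yet the neutrophil grades in SAP 18.2.3 are absolute. A baseline QTcF above 450 or 480 msec is not by itself an exclusion. Exclusion criterion 12 sets its limit at 500 msec, although it also covers patients at high risk of QT prolongation, so how many enter with such values is unknown.

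There is no control arm against which baseline abnormality would cancel. The initial analysis after 100 patients may be used to consider approval, so the incidence tables need to mean what their label says.

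**Working it through.** The documents give no rate, sample size or power for these tables, so there is no plan figure to reproduce. The check has two parts.

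**1. Which criteria are exposed.**

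- No baseline term, so affected: haemoglobin (anaemia), platelets, neutrophils, white cells, albumin; QTcF above 450, 480 and 500 msec; systolic and diastolic pressure, pulse and temperature.
- Baseline-referenced, so not affected: ALT, AST, ALP, GGT and bilirubin, whose grades switch to multiples of baseline when baseline is abnormal; the QTcF change categories, such as "> 30 msec increase from Baseline"; and percentage change in weight.

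**2. Size of the distortion for an exposed criterion.** All inputs are assumptions:

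- b = share already past the threshold at baseline
- r = true new-onset rate among the others
- s = share of baseline-abnormal patients still abnormal after dosing

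Every patient is taken to have a baseline and a post-dose value.

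Reading A counts any post-dose abnormality over all evaluable patients: b·s + (1 − b)·r.
Reading B counts only new abnormalities over all evaluable patients: (1 − b)·r.
Target: new abnormalities among patients not already past the threshold, which is r.

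With r = 20%:

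| b | A, s = 100% | A, s = 50% | B | Target |
|---|---|---|---|---|
| 10% | 0.10 + 0.18 = 28% | 0.05 + 0.18 = 23% | 18% | 20% |
| 30% | 0.30 + 0.14 = 44% | 0.15 + 0.14 = 29% | 14% | 20% |
| 50% | 0.50 + 0.10 = 60% | 0.25 + 0.10 = 35% | 10% | 20% |

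In counts, take the planned enrolment of about 200 with b = 20%, r = 10% and s = 100%. Then 40 patients are abnormal at baseline and 16 of the other 160 become abnormal. Reading A gives 56/200 = 28%, reading B gives 16/200 = 8%, and the target is 16/160 = 10%.

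Over b from 5% to 50%, r from 5% to 20% and s from 50% to 100%, reading A is 1.07 to 10.5 times the true new-onset rate. Reading B is 0.95 to 0.50 times it.

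**Vital-sign labels.** This needs no arithmetic. One cut-off on pulse rate carries three rhythm names, and pulse rate alone cannot tell them apart. With no low limit for blood pressure and a default of normal, every low systolic or diastolic reading is classed as normal in this table.

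**The case against.** Several points on the other side stand.

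- **The rule is inherited.** A reader might infer that the SAP departed from the protocol on who is at risk. It did not: the rule that one post-dose value is enough is in protocol 8.9.3. What the SAP omits is the newly-occurring condition. Restoring that alone would still leave the denominator wrong.
- **The direction of error is not fixed.** It is tempting to conclude that baseline disease will be reported as drug toxicity. The SAP still calls these abnormalities treatment-emergent, and the protocol defines that as started or worsened. If that definition carries over, stable baseline abnormalities are not counted and the error is dilution.
- **Not every table is affected.** The main liver tests, QTcF change and weight criteria already use baseline.
- **Other outputs help.** SAP 18.2 plans laboratory shift tables by CTC grade and by normal range. Change-from-baseline summaries are planned for laboratory, ECG and vital signs, with QTcF change categories and individual QTcF plots. It would be too strong to say that a drug signal cannot be separated from underlying disease. However, the only ECG shift table uses the investigator's overall judgement, and SAP 18.4 lists no shift table for vital signs.
- **Some text is not visible.** SAP 18.2.4 and parts of 3.3 are redacted, and the table templates are separate, so a laboratory rule could exist there. The readable ECG and vital-sign sections contain none.
- **The vital-sign cut-offs are partly a clinical choice.** The SAP version history says the systolic limit followed advice from safety physicians. The high limits are not challenged here. Nor do the documents show that a separate ventricular tachycardia row will be printed, since the three labels share one cell. Clinically significant vital-sign abnormalities are still captured as adverse events.

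**Conclusion.** The concern holds for criteria with no baseline term. The stated denominator is wrong for a new-onset rate under either reading of the numerator, and the readable SAP text does not say which reading applies. With an assumed 20% new-onset rate and 10% to 50% abnormal at baseline, the reported figure could lie anywhere from 10% to 60%. These sizes are illustrations: b, r and s are assumed, and the upper figures require every baseline abnormality to persist.

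The problem is clearest for absolute QTcF and vital signs, where no category shift table would reveal it, and milder for laboratory tests, where the CTC shift tables partly reveal it. The pulse labels and the default of normal for low blood pressure are separate reporting faults in SAP 18.4.2. The change should be made before the tables are programmed for reporting, but nothing here shows that the safety conclusions would be wrong.

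**What to change.** In SAP 18.2.3, 18.3.2 and 18.4.2, for each absolute criterion:

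1. Define at risk as patients with a baseline value not already in that or a worse category, and at least one post-dose value.
2. Count a patient only when a post-dose category is worse than the baseline category.
3. Show patients already abnormal at baseline, and those with no baseline value, in separate rows.

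Add tables of baseline category against worst post-baseline category for QTcF and vital signs. Either align protocol 8.9.3 with the new denominator or list the change in SAP 3.3.

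In SAP 18.4.2, replace the three pulse labels with one: tachycardia, rhythm not determined. Add a low category for systolic and diastolic pressure for reporting, with the cut-off set by the sponsor's safety physicians, so that low values are not normal by default.

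The cost is some SAP wording and a baseline condition in the table programs, using data already collected. The downside is that denominators will differ slightly from row to row, so each row should print its own.

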18.3. ECG EVALUATIONS

Results for 12-lead electrocardiograms (ECGs) will be included in the reporting of this study.

The following ECG parameters will be reported for this study:

- Heart Rate (bpm)
- PQ Interval (PR) (msec)
- RR Interval (msec)
- QRS Interval (msec)
- QT Interval (msec)
- QTcF – Fridericia’s formula (msec)
- Overall assessment of ECG (Investigator’s judgment):

Normal

Abnormal, Not Clinically Significant (ANCS)

Document: \\weedc-vnasc01\BIOSdata\F2G\F901318 [REDACTED]
Author: [REDACTED] Version Number: 3.0
Version Date: 06Apr2023
Template No.: CS_TP_BS016 Revision 6 Reference: CS_WI_BS005
Effective Date: 02Dec2019

[REDACTED]

Abnormal, Clinically Significant (ACS)

The following summaries will be provided for ECG local and central overread data:

- Table and box-and-whiskers plot of actual and change from baseline value descriptive statistics by visit (for quantitative measurements)
- Shift from baseline in overall assessment of ECG (Investigator’s judgment)
- Incidence of treatment-emergent markedly abnormal criteria
- Listing of ECG data

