
- Overall incidence of:
 - AEs.
 - Serious AEs (SAE) (including deaths).
 - AEs leading to premature treatment discontinuation.
 - AEs leading to premature study withdrawal.
 - AEs by relationship.
 - AEs by severity (common terminology criteria for adverse event [CTCAE] grade).
 - AEs of Special Interest (AESI).
- Changes from baseline during the treatment period and at FU in:
 - Vital signs (including weight and body mass index [BMI]).
 - Clinical laboratory assessments and incidence of pre-defined abnormalities.
 - Electrocardiogram (ECG) results and incidence of pre-defined abnormalities.
 - Physical examination findings.
- [REDACTED].
- Changes in concurrent medication dose and/or frequency resulting from potential DDIs.
- Overall exposure, individual dose modification, dose intensity.

Pharmacokinetics:

- PK data (C_{min} ; C_{max} , T_{max} , $AUC_{0-\tau}$, CL/F and Vz/F).
- Effect of concomitant medication on PK profiles.

Statistical Methods:

Sample Size Determination:

This is an open-label study, with no randomization or stratification. There is no upper limit to the enrolment of patients with culture-proven infections. [REDACTED]

[REDACTED]. Total enrolment into the study is anticipated to be approximately 200 patients. This will enable patients who have no suitable treatment options for their invasive fungal disease and are ineligible for the Phase III trial to enrol into Study 32 and receive treatment with F901318.

F901318 has been granted Breakthrough Therapy Designation by the FDA based on preliminary clinical evidence that demonstrates F901318 may provide substantial improvement over available therapy. As this designation is intended to expedite the development and review of important products, an initial analysis of data will be performed when 100 patients have completed treatment, to enable the Sponsor to formally consider the possibility that initial approval might be achieved based on the data for the population of patients with limited or no treatment options for life-threatening fungal infections.

Analysis Sets:

The analysis sets to be used in this study are:

- All Patients Enrolled analysis set: all patients who provide written informed consent.
- Safety analysis set (SAF): consists of all patients who receive at least one dose of study drug (or part thereof). The SAF will be used for the analysis of all safety data.

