 - r. Within 4 weeks prior to screening. See also Section 6.4.2.2: neutropenia is defined as $ANC < 0.5 \times 10^9/L$ [$< 500/mm^3$]. Neutropenia status will be recorded from the screening visit throughout the 4-week post treatment period. Neutropenic episodes supporting the Host Factor criteria of "Neutropenia" at the time of the initial diagnosis of the invasive fungal infection should also be reported. Absolute neutrophil count results from 4 weeks prior to screening through the patient's last study visit and any values supporting the Host Factor Criteria Neutropenia. Local Laboratory ANCs for all neutropenic episodes (defined as $ANC < 0.5 \times 10^9/L$ [$< 500/mm^3$]) from 4 weeks prior to screening up to the end of study and those that support a Host Factor Criteria of Neutropenia at the time of the initial diagnosis (which may be greater than 4 weeks prior to Screening). ANC results to cover the period from onset up to and inclusive of the first 2 consecutive ANC values $> 0.5 \times 10^9/L$ on consecutive days confirming resolution of the episode. When differentials are not performed due to insufficient WBCs, the total WBC count for the day should be recorded.
 - s. The Screening EQ-5D-5L questionnaire provides the baseline, and should be completed as close to the day prior to the start of treatment as is feasible.
 - t. Only in patients with abnormalities observed at main study phase EOT.

- u. See Table 7 and Appendix 3 for minimum list of tests to perform. Additional samples at unscheduled visits should also be taken if ALT/AST or bilirubin elevations occur (see Appendix 3). [REDACTED] Blood sampling for evaluation of liver function must always be consistent with the Liver Biochemistry Management Algorithm as described in Appendix 3.
- v. Systolic blood pressure, diastolic blood pressure, pulse rate and body temperature; body temperature should be measured via the same route throughout the study period. Vital signs should be measured before study drug administration.
- w. ECG on treatment should be performed between 30 min and 4 hours after dosing.
- x. [REDACTED]

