6.4.3.2 Physical Examination

A physical examination should be conducted at the timepoints shown in Table 1 and at any other time during the study when clinically indicated, as determined by the Investigator. The following body systems/areas should be examined: head, eyes, ears, neck, trunk, respiratory,

cardiovascular, gastrointestinal, musculoskeletal, neurological, endocrine/metabolic, lymphatic/haematologic, dermatological, psychological, genitourinary and other (to be specified). Any new abnormalities or worsening of existing abnormalities must be recorded in the eCRF as AEs.

Physical examination will not be recorded during ET, unless clinically indicated or associated with an AE.

6.4.3.3 *Electrocardiogram*

A 12-lead electrocardiogram (ECG) recording will be obtained at the timepoints shown in Table 1. For patients receiving study drug (i.e., Day 1 onwards), the ECG assessment should be conducted between 30 minutes and 4 hours after oral dosing. All patients must also have an ECG at the main study phase EOT. At the Post-treatment Follow-up visit, ECG recordings will only be required for patients with abnormalities observed at the main study phase EOT.

Each abnormality observed on ECG must be reported and, if not related to the underlying disease, must be confirmed as clinically not significant or repeated at intervals determined by the Investigator until they return to baseline levels. Abnormalities should be reported as AEs in the eCRF only if they result in a clinically relevant condition, as determined by the Investigator. Each ECG recording is to be signed and dated by the Investigator or his designee.

Additional monitoring may be required if a QT-prolonging medication is initiated during the course of the study. See Section 5.9.1.1 for details.

Study-related ECGs are not required during ET, unless clinically indicated or associated with an AE.

6.4.3.4

[REDACTED]

[REDACTED]

[REDACTED]

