8.9.4.2 ECG

ECG results will be summarised using descriptive statistics at each visit for observed data and change from baseline.

Pre-defined QT interval treatment-emergent abnormalities, as defined by CTCAE criteria, will be presented in tables and listed, where the incidence rate will be based on the total number of patients 'at risk' (see example in Section 8.9.3).

A similar approach as for laboratory values will be followed for ECG with regards to retests and values not complying with CTCAE criterion.

Change from baseline to each post-baseline visit, main study phase EOT and EOS in Investigator-judged abnormal classification will be presented as shift tables:

- Abnormal and clinically significant
- Abnormal and not clinically significant
- Normal.

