7.2. MISSING DATA

Summary statistics will be presented for observed data only. If a Baseline value is missing, no change from Baseline will be calculated. Missing data will be presented as part of a “Missing” category or statistic, if relevant.

Missing safety data will not be imputed.

Missing efficacy data will be handled as described in [section 16](#) of this SAP. Missing PK data will be handled as described in [section 17](#) of this SAP.

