Completed	XX (XX.X%)	XX (XX.X%)	XX (XX.X%)
Discontinued	XX (XX.X%)	XX (XX.X%)	XX (XX.X%)
Reasons for Discontinuation: XXXXXXXXXXXXX XXXXXXXXXXXXX	XX (XX.X%) XX (XX.X%)	XX (XX.X%) XX (XX.X%)	XX (XX.X%) XX (XX.X%)

SOURCE: Listing 16.2.1.1
Abbreviations / definitions
Formulae
F-values...
Symbols...
NOTE 1: Treatment A=XXXXXXXXXXXXXXXXXXXXX.
 B=XXXXXXXXXXXXXXXXXXXXX.
NOTE 2: ...

Page 1 of 1

- X:\CUSTOMER\COMPOUND\STUDY\BIOSTATISTICS\PRODUCTION\TABLES\T14_1_1_1_SAS.DDMMYYYY HH:MM

DATES & TIMES

Depending on data available, dates and times will take the form DDMMYYYY:hh:mm.

SPELLING FORMAT

English UK.

PRESENTATION OF VISITS

For outputs, visits will be represented as follows and in that order:

Long Name (default)	Short Name
Screening (Visit 1)	Screening
Baseline ^a	Baseline
Day 1 (Visit 2)	Day 1

Document: \\weedc-vnasc01\BIOSdata\F2G\F901318_____

Author: _____ Version Number: 3.0

Version Date: 06Apr2023

Template No.: CS_TP_BS016 Revision 6 Reference: CS_WI_BS005

Effective Date: 02Dec2019

F2G Ltd.
PROTOCOL F901318/0032

Long Name (default)	Short Name
Day 2 (Visit 3)	Day 2
Day 3 (Visit 4) * Day 3-5 will be presented under Day 3 (Visit 4)	Day 3
Day 5 (Visit 5)	Day 5
Day 7 (Visit 6) * Day 6-8 will be presented under Day 7 (Visit 6)	Day 7
Day 10 (Visit 7) * Day 9-11 will be presented under Day 10	Day 10
Day 14 (Visit 8)	Day 14
Day 17-18 (Visit 9)	Day 17-18
Day 21 (Visit 10)	Day 21
Day 24-25 (Visit 11)	Day 24-25
Day 28 (Visit 12)	Day 28
Day 35 (Visit 12a)	Day 35
Day 42 (Visit 13)	Day 42
Day 49 (Visit 13a)	Day 49
Day 56 (Visit 14)	Day 56
Day 70 (Visit 15)	Day 70
Day 84 (Visit 16)	Day 84
CRF End of Treatment (Visit 17)	CRF EOT

Document: \\ieedc-vnasc01\BIOSdata\F2G\F901318\ [Redacted]
 Author: [Redacted] Version Number: 3.0
 Version Date: 06Apr2023
 Template No.: CS_TP_BS016 Revision 6 Reference: CS_WI_BS005
 Effective Date: 02Dec2019

F2G Ltd.
PROTOCOL F901318/0032

Long Name (default)	Short Name
Derived End of Treatment ^b	DER EOT
Follow-up 4 Weeks after End of Treatment (Visit 18)	FU 4 WKS EOT
Unscheduled Visit XX.XX ^c	UNSCH XX.XX
Start of Extended Treatment ^d	ST EXT TRT
Extended Treatment Visit XX ^d	EXT TRT VXX
End of Extended Treatment ^d	END EXT TRT
Follow-up 4 Weeks after End of Extended Treatment ^d	FU 4WKS END EXT TRT

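### The 4-week follow-up ECG row describes mainly patients selected for an abnormal End of Treatment ECG, but the by-visit ECG displays neither restrict nor label it

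*SAP*

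**What the plan says.** **Collection.** Protocol 6.4.3.3 (Electrocardiogram) sets different rules for the last two visits. At EOT: "All patients must also have an ECG at the main study phase EOT". Four weeks later: "At the Post-treatment Follow-up visit, ECG recordings will only be required for patients with abnormalities observed at the main study phase EOT". SAP 3.1 adds that patients who go on to extended treatment do not have the main-phase 4-week follow-up assessment.

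**Analysis.** The protocol synopsis lists ECG results among the safety criteria under "Changes from baseline during the treatment period and at FU in". Protocol 8.9.4.2 then states: "ECG results will be summarised using descriptive statistics at each visit for observed data and change from baseline". It also asks for shift tables of the Investigator's ECG classification from baseline to each post-baseline visit. SAP 18.3 carries this forward for local and central overread data as a "Table and box-and-whiskers plot of actual and change from baseline value descriptive statistics by visit (for quantitative measurements", plus a shift from baseline in the overall assessment.

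**Handling.** SAP 6.4 fills by-visit summaries with whatever was recorded at the nominal visit. SAP 7.2 says "Summary statistics will be presented for observed data only". Visit 18, the 4-week follow-up, is one of the visits to be shown in outputs (SAP Appendix 1, Presentation of Visits).

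**What is absent.** SAP 18.3 does not restrict, label or pair the follow-up row. SAP 18.3.1 gives no ECG derivations, and SAP 3.3 records no departure on this point. For the efficacy responses, by contrast, the SAP does state who counts at the 4-week follow-up (for example SAP 16.1.5.1).

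**The concern.** Taken together, these rules put two populations in adjacent rows of one table. The EOT row covers everyone with an EOT ECG. The follow-up row covers mainly those whose EOT ECG was abnormal, without the patients who continued treatment.

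The follow-up row invites a particular reading. It answers a listed safety endpoint, and it falls well after the drug is gone: with the 24 to 30 hour half-life in protocol 4.2, 28 days is 672/30 = 22 to 672/24 = 28 half-lives. A reader will naturally compare it with EOT to judge whether ECG findings resolve. Set against the all-patient EOT row, the selected group can look as if values stay high or rise after stopping. Followed within the selected patients, a fall from EOT can look like recovery when part of it is regression to the mean. The follow-up column of the shift table is the plainest case: patients enter it because of an ECG abnormality, and it reports the percentage with an ECG abnormality.

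**Working it through.** The plan states no figure here, so there is nothing to reproduce. The check traces who is in each row, then illustrates size with labelled assumptions.

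1. **Who is in each row.**
   - EOT: all patients (protocol 6.4.3.3).
   - Follow-up: required only if abnormal at EOT (6.4.3.3); not applicable to extended-treatment patients (SAP 3.1). The Amendment 04 rationale in protocol Appendix 4 puts extended treatment at roughly 25% of enrolled patients, so this second exclusion is not trivial.
   - Optional extra ECGs are possible, because the protocol says only when one is required. Hence *mainly* selected, not wholly.

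2. **Direction for actual values.** Let p be the share abnormal at EOT, and m_A and m_N the follow-up means that EOT-abnormal and EOT-normal patients would show if all were tested. The all-patient follow-up mean is p·m_A + (1−p)·m_N, and the row shows m_A. The excess is m_A − [p·m_A + (1−p)·m_N] = (1−p)·d, where d = m_A − m_N at follow-up. It is zero only if the two groups have equal means at follow-up. With assumed p = 0.5 and d = 10 msec it is 0.5 × 10 = 5 msec; with p = 0.2 and d = 30 msec it is 0.8 × 30 = 24 msec.

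3. **Illustrative simulation (every input is assumed).** One million patients per scenario; QTcF mean 420 msec; between-patient SD 15 or 25; within-patient SD 8 or 15; drug effect at EOT 0 or 5 msec, gone by follow-up. A follow-up ECG is taken only if EOT is abnormal. Abnormal means either QTcF above 450 msec alone, or that plus a 30% chance of an abnormality unrelated to QTcF.

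| Abnormal at EOT means | Share in follow-up row | Row mean minus all-patient follow-up mean | Above 450 msec at follow-up: row | Above 450 msec at follow-up: all patients |
|---|---|---|---|---|
| QTcF > 450 only | 3.9–19.6% | 17.6–39.1 msec | 25.4–71.8% | 3.9–15.2% |
| That, or unrelated abnormality (30%) | 32.6–43.7% | 2.4–10.1 msec | 7.2–26.6% | 3.9–15.2% |

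4. **Change from baseline.** In the same model, mean change from baseline at follow-up lies between −0.1 and +0.1 msec in every scenario, for the selected group and for all patients. The drug effect is assumed gone, and baseline and follow-up errors behave alike. A difference would appear if the EOT abnormality, or its cause, persisted.

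5. **Within the selected patients.** With no drug effect and selection on QTcF alone, EOT sits 4.0 to 19.8 msec above baseline and follow-up is back at baseline. That apparent recovery is produced by selection.

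**The case against.** The strongest reply is that this is one row of a descriptive safety table. No objective or test concerns reversibility. The printed n will show the drop between EOT and follow-up. SAP 18.3 also lists all ECG data, and SAP 18.3.2 adds a spaghetti plot of QTcF for the central reads. The table templates mentioned in SAP 8 are not part of the public documents and may carry a footnote. Selection is on any ECG abnormality, not on QTcF, so the effect on QTcF may be small. Finally, the protocol asks for summaries at each visit and for change at follow-up, so simply deleting the row would depart from it.

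Most of this limits the size of the point without removing it. A smaller n shows that patients are missing, not that they were left out for being normal. Listings and individual plots do not correct a by-visit mean, a box plot or a percentage. The broad meaning of abnormal can weaken the effect on QTcF (second line of the table), but it does nothing for the overall-assessment shift, where selection and outcome are the same kind of judgement. The point about the each-visit wording stands, and the fix has to deal with it openly.

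**Conclusion.** The point holds as a matter of presentation and interpretation. As written, the plan sets a follow-up group selected mainly for EOT abnormality beside an all-patient EOT row, with no SAP text that says so. Actual values, box plots and the percentage abnormal in the shift table are clearly affected. Change from baseline is affected only if the abnormality persists. The documents supply neither the QTcF distribution nor the share abnormal at EOT, so the 2 to 39 msec range rests entirely on assumptions. The primary analysis, the EOT results and the on-treatment summaries are untouched.

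Four stronger readings might be inferred, and the documents do not support them:
- *The follow-up ECG is the only off-drug ECG information.* Patients who stop early after success still attend Days 42 and 84 (protocol 5.1). Whether ECGs are taken then cannot be checked, because the Table 1 rows are redacted.
- *The distortion approaches the SAP's own category of more than 30 msec.* That category in SAP 18.3.2 is an individual's increase from baseline; the figures above are differences between group means of actual values.
- *The table will carry no warning.* The SAP text requires none, but the templates are not available.
- *Table 1 footnote t repeats the ECG restriction.* Its wording, "Only in patients with abnormalities observed at main study phase EOT", fits, but the row it belongs to is redacted. Protocol 6.4.3.3 is sufficient without it.

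**What to change.** In SAP 18.3, for both local and central overread data:

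- Take the 4-week follow-up visit out of the by-visit ECG table, the box plots and the all-patient shift table.
- Replace it with one table of baseline, EOT and follow-up values for QTcF and overall assessment, paired within patients who were abnormal at EOT and have a follow-up ECG. Title it as that subset and give its n.
- Count separately the patients without a follow-up ECG: normal at EOT, entered extended treatment, or other reasons. Merging the first two would wrongly suggest that extended-treatment patients were not re-tested because they were normal.
- Note under the table that some fall from EOT is expected from selection alone. This is why the baseline column is needed.

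Record the change in SAP 3.3 as a departure from the each-visit wording of protocol 8.9.4.2. Change at follow-up is then still reported, for the group in which it is mainly measured. If the sponsor prefers to keep the visit in the by-visit table, the minimum is a footnote on that row stating how its patients were selected.

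The cost is one replaced descriptive table, a short addition to SAP 18.3 and an entry in SAP 3.3. No further ECGs are needed.
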